9.7 Treatment of Outliers in Pharmacokinetic Analysis

If a value is considered to be anomalous due to being inconsistent with the expected PK profile, it may be appropriate to exclude the value from the PK analysis. However, the exclusion of any data be fully documented in the DRR and discussed in the CSR.

Any quantifiable predose concentration value will be considered anomalous and set to missing for the PK analysis. This will be set to 0 by default within Phoenix WNL.

9.8 Presentation of Pharmacokinetic Data

For plasma whole blood and urine concentration data, the following rules will apply:

- Values that are BLQ will be set to 0 for the calculation of summary statistics. In listings BLQ values will be reported as “<LLQ” where LLQ will be replaced with the value for the lower limit of quantification
- Arithmetic mean or median values that are BLQ will be presented as 0.

- If any BLQ results (treated as 0) are in a series of summarized data, geometric mean and CV% of geometric mean will be reported as not calculated (NC).

For PK parameters the following rule will apply:

- Geometric mean and coefficient of variation will not be calculated for t_{last} and t_{max} .

Concentration (mass equivalent in mL or mass in mL)/time curves for plasma total [^{14}C], [^{14}C]-CHF6001 and non-radiolabelled CHF6001 will be presented in linear/linear and log/linear scale. Plots will be presented based on arithmetic means and by subject i.e. all individual plasma concentration/time curves will be presented in one graph.

Arithmetic means (+ SD) showing [^{14}C]-total recovery (Fe_f, Fe_u, Fe_tot in the same graph) and ^{14}C -CHF6001 recovery (Fe_f, Fe_u, Fe_tot in the same graph) over the time will be presented using line charts.

All individual concentration data (mass equivalent per mL or mass per mL) and PK parameters will be listed.

In addition, a listing of the actual sampling times relative to drug inhalation will be provided. Concentrations will be summarized by scheduled sampling time by using n, arithmetic mean, SD, CV, median, minimum and maximum.

For each applicable listing, appropriate flag will be added in case of a concentration reported as ND (i.e., not done) or NS (i.e., no sample) or of value BLQ or for PK parameters not estimated / Not calculated.

10 Safety Analyses

10.1 Extent of Exposure

Not applicable since this is a single dose study.

10.2 Adverse Events

An AE will be classified as pre-treatment AE if it starts after the informed consent signature and before the time of first inhalation of the study drug (date of informed consent < AE onset date and AE onset date-time < date-time of first study drug inhalation).

All adverse events starting on or after the time of first study drug inhalation will be classified as treatment emergent adverse event (TEAE) (date-time of first study drug inhalation \leq AE onset date-time \leq date of discharge).

An AE will be classified as a post-study AE if it starts after the date of discharge (AE onset date $>$ date of discharge).

An adverse drug reaction (ADR) is an AE judged as related to the study medication.

A serious ADR is a serious AE (SAE) judged as related to the study medication.

A severe AE is an AE with severe intensity.

An AE leading to discontinuation will be identified based on the information collected in study termination form (i.e. reason for discontinuation =Adverse event).

An AE leading to death is an AE with outcome equal to “Fatal”.

Pre-treatment AEs, TEAEs and post-study AEs will be presented separately. Pre-treatment AEs and post-study AEs will be presented in the listings only.

The number of TEAEs, drug-related TEAE, serious TEAE and TEAE leading to study discontinuation and the number and the percentage of subjects experiencing TEAEs, drug-related TEAEs, serious TEAEs and TEAEs leading to study discontinuation will be summarised.

The MedDRA SOC and PT will also be used for tabulation. The number and percentage of subjects with at least one AE and the number of AEs will be presented by SOC and PT for the above categories of AEs.

Derived variables presented in the listings:

The relative day of AE onset will be calculated as follows:

- for pre-treatment AEs:
 - AE onset date - date of first inhalation of study drug (if AE onset date is completely known);
 - missing (if AE onset date is incomplete or unknown).
- For TEAEs and post-Study AEs:
 - AE onset date – date-time of first inhalation of study drug +1 (if AE onset date is completely known);
 - missing (if AE onset date is incomplete or unknown).

The duration of an AE (hours) will be calculated as follows:

- $(AE\ end\ date-time - AE\ onset\ date-time) / 3600$ (when both date-time are completely known)

The duration of an AE (days) will be calculated as follows:

If duration in hours ≥ 24 hours:

- AE end date – AE onset date +1 (when both dates are completely known);
- date of completion/discontinuation – AE onset date + 1 (when the AE onset date is fully known but the AE is not resolved at the end of the trial): in this case the duration will be presented as “>x days” in the listing rather than “x days”;
- missing (when the AE onset date is incomplete or unknown, or when the AE has resolved but with an incomplete or unknown end date, or when the AE onset date is > date of completion/discontinuation and the AE is not resolved).

If duration in hours <24 hours:

- duration (hours)/24

Duration will be displayed in days with values <1 days in case of short term AE.

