### **Safety Variables**

- The number and percentage of subjects experiencing adverse events, adverse drug reactions, serious adverse events and adverse events leading to study withdrawal will be summarized.
- Percentage of subjects with clinical relevant changes at 2,5 hrs post-dose in SBP, DBP and HR (from 12-lead ECG) defined as
  - Change from pre-dose in DBP > 10 mmHg;
  - Change from pre-dose in SBP > 20 mmHg;
  - Change from pre-dose in HR > 20 bpmwill be summarized.
- For quantitative laboratory parameters (chemistry, haematology and fasting glucose), shift tables from screening with regards to normal range will be presented.

Clinical Study Code: CLI-06001AA1-02	Version No.: 1.0
EUDRACT No.: 2020-004201-31	Date: 19 October 2020

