### End of the trial

The end of the trial is defined at execution of the Follow-up call (or visit) of the last subject of the trial.

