### 7.1.3 Follow-up

A follow-up call will be performed from 7 to 10 days after the discharge to perform the following:

- CONCOMITANT MEDICATIONS CHECK: concomitant medications taken to treat AEs by the subjects since the discharge will be checked and recorded in eCRF.
- ADVERSE EVENTS RECORDING: the status of unresolved AEs/SAEs at the discharge will be checked and any new AEs/SAEs occurred after the discharge will be recorded in the eCRF.

This safety follow-up call shall also be performed in case of premature discontinuation (7-10 days from the last administration intake).

If needed, according to the investigator's opinion, a follow-up visit can be performed.

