### **10.8 Recording Adverse Events**

All Adverse Events occurring during the course of the study must be documented in the Adverse Event page of the electronic Case Report Form (eCRF). Moreover, if the Adverse Event is serious, the Serious Adverse Event Form must also be completed.

It is responsibility of the Investigator to collect all adverse events (both serious and non-serious) derived by spontaneous, unsolicited reports of subjects, by observation and by routine open questionings.

The recording period for Adverse Events is the period starting from the Informed Consent signature until the subject's study participation ends.

Clinically significant abnormalities detected at Screening not due to a pre-existing condition or clinically significant changes at the following visits in the medical opinion of the investigator must be reported as adverse events in the eCRF.

If a clinically significant abnormal laboratory finding or other abnormal assessment meets the definition of an AE, then the AE eCRF page must be completed, as appropriate. A diagnosis, if known, or clinical signs and symptoms if diagnosis is unknown, rather than the clinically significant abnormal laboratory finding, should be reported on AE eCRF page. If no diagnosis is known and clinical signs and symptoms are not present, then the abnormal finding should be recorded.

For pharmacovigilance purposes, all SAEs should be followed-up in order to elucidate as completely and practically as possible their nature and/or causality until resolution of all queries, clinical recovery is complete, laboratory results have returned to normal, stable condition is reached or until the subject is lost to follow-up. Follow-up may therefore continue after the subject has left the study. In this case, the follow-up will continue with no timelines for related SAEs, while for unrelated SAEs the type and extent of follow-up undertaken will be determined for each individual case and will depend upon the nature (e.g. events with poor prognosis or which do not resolve), severity and medical significance of the event.

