### 12.3.5 Safety variables

#### Adverse Events

All adverse events starting on or after the time of first study drug inhalation will be classified as treatment emergent adverse event (TEAE). Any adverse events started after the informed consent signature and before the time of first study drug inhalation will be classified as pre-treatment adverse event.

The number of subjects who experienced at least one TEAE, drug-related TEAE, serious TEAE and TEAE leading to study discontinuation will be summarized. Summaries will be presented overall (number and percentage of subjects having at least one event, total number of events) and by system organ class and preferred term (number and percentage of subjects having at least one occurrence of that event).

All adverse events will be listed.

Pre-treatment adverse event will be listed only.

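### The SAP ends the TEAE window at discharge without declaring it, so adverse events starting in the 7-10 day follow-up are left out of the summary tables

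*SAP*

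**What the plan says.** Protocol 12.3.5 has two classes of adverse event. For events after dosing it says: "All adverse events starting on or after the time of first study drug inhalation will be classified as treatment emergent adverse event (TEAE"). No end date is given. For events before dosing it says: "Pre-treatment adverse event will be listed only". TEAEs, drug-related TEAEs, serious TEAEs and TEAEs leading to discontinuation are to be summarised overall and by SOC and preferred term. The protocol outline makes the same promise without naming a window: "The number and percentage of subjects experiencing adverse events, adverse drug reactions, serious adverse events" and events leading to withdrawal are to be summarised.

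The protocol also provides for collecting events after discharge. At the follow-up call, under 7.1.3, "any new AEs/SAEs occurred after the discharge will be recorded in the eCRF". Section 10.8 says: "The recording period for Adverse Events is the period starting from the Informed Consent signature until the subject's study participation ends". Section 3 says: "The end of the trial is defined at execution of the Follow-up call (or visit) of the last subject of the trial".

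SAP 10.2 repeats the protocol's TEAE sentence, but the formula in brackets after it limits onset to the date of discharge. It then adds a class the protocol does not have: "An AE will be classified as a post-study AE if it starts after the date of discharge". On presentation it says: "Pre-treatment AEs and post-study AEs will be presented in the listings only". The SAP summary tables cover TEAE categories only. SAP 12 reports no departure from the protocol analysis.

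**The concern.** A group of events that the protocol summarises has become listing-only in the SAP, and the section meant to disclose such changes says there are none. The events are not outside the study: the protocol requires the site to ask about them, enter them in the eCRF and record them until participation ends. The name post-study does not fit either, since both documents end the trial at the last follow-up call or visit.

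Safety and tolerability is one of the four stated objectives. A drug-related or serious event with a known onset after discharge would be missing from the corresponding TEAE table. The tabulated counts can only equal or fall below those under the protocol definition. A reader of the report would have no notice that a narrower definition had been used.

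**Working it through.** There is no figure in the plan to reproduce. The check compares the two definitions and then counts days.

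**The two rules applied to the same events**

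| Onset of event | Protocol 12.3.5 | SAP 10.2 formula |
|---|---|---|
| After consent, before first inhalation | Pre-treatment, listed only | Pre-treatment, listed only |
| First inhalation to discharge date (Day 11) | TEAE, summarised | TEAE, summarised |
| After the discharge date, up to the follow-up call | TEAE, summarised | Post-study, listed only |

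Only the last row differs. SAP 10.2 also disagrees with itself there: its sentence makes a Day 12 event a TEAE, while its formula does not.

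The cut is by onset, not by when the event is found. An event first mentioned at the call that began on or before the discharge date remains a TEAE, because the post-study rule needs an onset date later than discharge. An incomplete onset date goes to the first class that the available parts of the date allow, and treatment emergent comes first (SAP 7.3.1). The loss therefore concerns events whose onset is known to be after discharge.

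**Inputs for the day count**
- Discharge on Day 11 (protocol 7.1.2).
- Follow-up call 7 to 10 days after discharge (protocol 7.1.3).
- Last PK sample 241.75 h after inhalation (protocol 7.2.1.1), with discharge soon afterwards.
- 8 subjects (protocol 12.1).

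**Calendar dates, which is how the SAP rule works**

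The call falls on Day 11 + 7 = Day 18 at the earliest and Day 11 + 10 = Day 21 at the latest. With f follow-up days, the share left out is f / (11 + f):
- f = 7: 7 / 18 = 0.389 (Days 12-18 of 18)
- f = 10: 10 / 21 = 0.476 (Days 12-21 of 21)

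**Elapsed time, as a second basis**

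241.75 / 24 = 10.07 days from inhalation to the last sample. The share is f / (10.07 + f):
- f = 7: 7 / 17.07 = 0.410
- f = 10: 10 / 20.07 = 0.498

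The two bases together give about 39% to 50%.

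**Effect on one table row**

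One subject of 8 is 1/8 = 12.5 percentage points. A row falls by that amount when an omitted subject has no other event in it. If the subject has another event in the row, the subject incidence does not change, although the event count does.

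**The case against.** This is an uncontrolled single-dose study in 8 subjects, with no tests, no confidence intervals and no decision rule that depends on TEAE incidence. Subjects are supervised on site until Day 11, so the tables cover the closely observed period. Later events are still recorded and listed, and with 8 subjects a reader can see each one. Protocol 12.3 leaves analysis detail to the SAP, and separating on-site from post-discharge events is a legitimate way to present them. All of this stands, and it limits the importance of the point. It does not justify a statement of no change, and a listing does not supply the counts that protocol 12.3.5 promises.

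The percentages can also be challenged. They are shares of time, and time ascertained by one phone call is not equivalent to residential observation. That is correct: the documents give no event rates, so the figures must not be read as the proportion of events lost. The calendar basis, 39% to 48%, matches the SAP rule more closely than elapsed time does.

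Finally, the SAP formula compares an onset date-time with a date, so the handling of Day 11 onsets depends on programming. The accompanying post-study rule, which requires an onset date later than discharge, supports treating them as TEAEs. Clearer wording would settle it.

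**Conclusion.** The concern holds. SAP 10.2 narrows the protocol's TEAE definition, moves events with known post-discharge onset to a listing-only class, and does not declare the change. For a completer discharged on Day 11 and called 7 to 10 days later, the tables omit onsets over 7 to 10 days. That is 39% to 48% of post-dose observation days by calendar date, or 41% to 50% by elapsed time. The number of events affected cannot be estimated from the documents and may be zero.

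This should be corrected, but it does not threaten the study. The events remain in the data and the listings, and the blood pressure, ECG and laboratory tables are unaffected.

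**What to change.** Preferred change: in SAP 10.2, define a TEAE as any adverse event with onset at or after first inhalation and up to the end of the subject's participation, meaning the follow-up call or visit. Remove the discharge cap and the post-study adverse event class. Then:

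- take the post-study class out of the allocation order for adverse events in SAP 7.3.1 and out of the relative-day rule in 10.2;
- check that the post-study classes for medications and procedures in SAP 8.4 and 8.5 still fit. They begin on the discharge date itself, whereas the adverse event class begins the day after;
- if the distinction is useful, add a flag to the listing for onset before or after discharge.

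Alternative: keep the class, add a summary table for it, and declare and justify the change in SAP 12.

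The preferred route costs some wording in 10.2 and 7.3.1, one changed derivation and a consistency check of 8.4 and 8.5. It needs no new data. The only downside is a possibly slightly higher TEAE count.

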10.3 Vital Signs

For the purpose of safety analyses, the mean of triplicate measurements of systolic blood pressure (SBP) and diastolic blood pressure (DBP) will be used. The mean SBP and DBP values at baseline and at 2.5 hours post- dose will be summarized using descriptive statistics. Change from baseline to 2.5 hours post-dose in mean SBP and DBP will also be summarized.

Number and percentage of subjects with clinically relevant changes from baseline to 2.5 hours post-dose in SBP and DBP will be summarized. Clinically relevant changes are defined as:

- Change from baseline in SBP > 10 mmHg
- Change from baseline in DBP > 20 mmHg

10.4 12-lead Safety Electrocardiogram

Triplicate ECG measurements will be averaged on available values and the average value will be used to calculate summary statistics for heart rate (HR), PR interval (PR), QRS interval (QRS) and QTcF interval (QTcF)..

Baseline value (i.e. pre dose value) and 2.5 hours post dose will be summarized.

Number and percentage of subjects with clinically relevant change in HR at 2.5 hours post-dose defined as change from baseline > 20 bpm, will also be summarized.

The number and the percentage of subjects with QTcF abnormalities defined as:

- QTcF >450 ms,
- QTcF >480 ms
- QTcF >500 ms;
- change from baseline to 2.5 Hours post dose in QTcF >30 ms
- change from baseline to 2.5 Hours post dose in QTcF >60 ms;

will be summarized.

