#### Vital signs

Percentage of subjects with clinical relevant changes from baseline to 2,5 hrs post-dose in SBP and DBP defined as

- Change from pre-dose in DBP > 10 mmHg;
- Change from pre-dose in SBP > 20 mmHg;

will be summarized.

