4.3 Other Variables

No other variables defined.

5 Sample Size

According to the exploratory nature of the study, no formal sample size calculation was performed. A total of 8 subjects will be included in the study to characterize the absolute bioavailability and the mass balance of CHF6001.

6 Analysis Sets

The definitions of the analysis sets are summarised below. A final agreement on the subjects to be included in or excluded from each analysis set will be reached during the Data Review Meeting (DRM) before the database lock. Inclusions and exclusions from analysis sets will be fully documented in the Data Review Report (DRR).

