7.8 Definitions

7.8.1 Baseline and Change from Baseline

Baseline values are defined as the last evaluation before the first treatment dose (Inhalation).

For each of the above variable, change from baseline is defined at each post-dose as:

Post-dose value – baseline value.

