10.5 Laboratory Data

Quantitative chemistry and haematology parameters and fasting glucose values will be summarized descriptively at screening and discharge. Shift tables from screening with reference to normal ranges will be presented.

Serology and urinalysis results will only be listed.

Abnormal laboratory data will be flagged in the listings.

11 Other Analyses

No other analyses planned.

12 Changes in the Planned Analyses from Study Protocol

There are no changes to the protocol defined analysis.

13 Output

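### SAP 10.3 swaps the protocol's blood-pressure cut-offs for clinically relevant change (SBP >10, DBP >20 mmHg instead of SBP >20, DBP >10 mmHg) and does not declare the difference

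*SAP*

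**What the plan says.** The protocol defines the flags in the outline (Safety Variables) and again in section 12.3.5 (Vital signs), identically. For diastolic pressure the rule is "Change from pre-dose in DBP > 10 mmHg"; for systolic pressure it is "Change from pre-dose in SBP > 20 mmHg". Both are assessed at 2.5 hours after the inhaled dose.

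SAP 10.3 plans the same table: "Number and percentage of subjects with clinically relevant changes from baseline to 2.5 hours post-dose in SBP and DBP will be summarized". Its definitions are "Change from baseline in SBP > 10 mmHg" and "Change from baseline in DBP > 20 mmHg".

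SAP section 12, where departures from the protocol are to be recorded, says: "There are no changes to the protocol defined analysis".

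**The concern.** The two documents use the same pair of numbers but attach them to opposite parameters, and the SAP says that nothing has changed. Safety and tolerability is a stated objective. Blood pressure is measured only once after dosing, and these flags are the only threshold-based blood-pressure analysis. The SAP is the programming specification, so the table would carry the protocol's label of clinical relevance while counting a different set of subjects.

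The described checks are not designed to catch this. SAP 13.4 provides for independent programming and comparison with the table shells, but describes no check against the protocol. SAP section 1 promises an explanation in the study report only for deviations from the SAP, and a table run as the SAP specifies would not be one.

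**Working it through.** **Are the definitions otherwise comparable?** The time point is 2.5 hours in both documents. The protocol refers to change from pre-dose and the SAP to change from baseline, but SAP 7.8.1 sets baseline as the last evaluation before the inhaled dose, so these coincide when the pre-dose value is available. SAP section 1 says it is based on protocol version 1.0 of 19 October 2020, the version reviewed here. The heart-rate cut-off (>20 bpm) is the same in both. Only the blood-pressure cut-offs differ.

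| Parameter | Protocol outline and 12.3.5 | SAP 10.3 |
|---|---|---|
| SBP change | > 20 mmHg | > 10 mmHg |
| DBP change | > 10 mmHg | > 20 mmHg |

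**Who is classified differently?** This part needs no assumption.

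| Change SBP/DBP (mmHg) | Protocol flags | SAP flags |
|---|---|---|
| +15/+5 | none | SBP |
| +5/+15 | DBP | none |
| +15/+15 | DBP | SBP |
| +25/+15 | SBP and DBP | SBP |

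For each parameter, the subjects who change status are exactly those with a change above 10 and up to 20 mmHg. The SAP can only flag as many or more subjects for SBP, and as many or fewer for DBP.

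**How often might it matter?** The plan has no figure to reproduce: it involves no hypothesis test, and "no formal sample size calculation was performed". The documents also give no SD for blood-pressure change, so the SDs below are assumptions. Take a mean change of zero, a normal distribution, and signed changes (SAP 7.8.1 defines change as post-dose minus baseline). Then P(change > c) = 1 − Φ(c/SD).

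| Assumed SD (mmHg) | P(>10) | P(>20) | Ratio |
|---|---|---|---|
| SBP 6 | 4.8% | 0.04% | about 110 |
| SBP 8 | 10.6% | 0.62% | about 17 |
| SBP 10 | 15.9% | 2.28% | 6.97 |
| SBP 12 | 20.2% | 4.78% | about 4.2 |
| DBP 4 | 0.62% | ~0 | very large |
| DBP 6 | 4.8% | 0.04% | about 110 |
| DBP 8 | 10.6% | 0.62% | about 17 |
| DBP 9 | 13.3% | 1.31% | about 10 |

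For SBP the SAP uses the P(>10) column and the protocol the P(>20) column; for DBP it is the reverse.

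For the 8 planned subjects, the chance of at least one flag is 1 − (1 − p)^8 and the expected number is 8p. In the middle of the range:

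- SBP, SD 8: at least one flag 1 − (1 − 0.1056)^8 = 59% under the SAP, against 1 − (1 − 0.0062)^8 = 4.9% under the protocol. Expected flags are 0.85 against 0.05.
- DBP, SD 6: at least one flag 0.3% under the SAP, against 32% under the protocol. Expected flags are 0.003 against 0.38.

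**The case against.** The case for treating this lightly is that it affects one descriptive table in 8 open-label healthy subjects. No test, confidence interval, PK parameter or mass-balance result depends on it, and the documents tie no dosing or stopping decision to these flags. SAP 10.3 also summarises SBP and DBP values and their changes, and SAP 7.10 lists all eCRF data, so a reader could recover the protocol-defined counts. All of that stands. It limits the harm, but the reported percentages would still not be the protocol's.

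The fold-changes depend on assumed SDs and are ratios of small probabilities: the systolic ratio falls to about 4 at SD 12 and the diastolic ratio to about 10 at SD 9. In the middle of the range the expected count moves by less than one subject for either parameter. That also stands, and it is why the exact statement about changes above 10 and up to 20 mmHg carries the point.

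A slip is inferred rather than shown. The no-changes statement in SAP section 12 is weak evidence of intent, because other differences are also undeclared. The adjusted R² criterion is 0.85 in protocol section 8 and 0.7 in SAP 9.2, and SAP 10.4 adds QTcF categories that the protocol does not have. The order of the lines does fit a slip: the protocol lists DBP first, the SAP lists SBP first, and both give 10 and then 20. Whatever the cause, the SAP contradicts the protocol and its own section 12.

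Finally, neither document justifies either pair of cut-offs clinically, and the table shells were not available to check. The finding is that the SAP does not count the subjects the protocol defines; it makes no judgement about which cut-offs are medically better.

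**Conclusion.** The concern holds. SAP 10.3 reverses the protocol's blood-pressure cut-offs without declaring it, and the section 12 statement is incorrect on this point. The direction is certain: a wider systolic flag and a narrower diastolic flag than the protocol specifies. The size is illustrative and rests on zero mean change, normality and SDs that are not in the documents. Over SBP SDs of 6 to 12 mmHg, the per-subject chance of a systolic flag is about 4 to 110 times the protocol's. Over DBP SDs of 4 to 9 mmHg, the chance of a diastolic flag is lower by a factor of about 10 or more. The consequence is confined to one safety table, but that table would be wrong against its own prespecified definition.

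**What to change.** Change the two lines in SAP 10.3 to the protocol's definitions (DBP change >10 mmHg, SBP change >20 mmHg), and check that the table shells and programs agree. If the sponsor intended different cut-offs, record the change and its reason in SAP section 12 so that the two documents are reconciled. Protocol 12.3 allows the SAP to be updated before database lock. The cost is two lines of text and the table program; no data collection or other analysis changes.
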